5.2.2 Nutritional Supplementation

The nutritional status of patients affected by bladder cancer is directly influenced by the presence of cancer which has an impact on all aspects of intermediary (protein, carbohydrate, lipid, trace element, and vitamin) metabolism, and by other factors such as age, adjuvant cancer therapy and stage of the disease^{16,17}. In addition, a patient who is undernourished before surgery has greater risk of morbidity and mortality¹⁸. The primary goal of nutrition therapy during the perioperative period is to optimize nutrient stores preoperatively and provide adequate nutrition to compensate for the catabolic response of surgery post-operatively. This includes preventing the loss of lean body mass, something that is increasingly recognized as a therapeutic target for cancer care.

At the time of consent, patients will be instructed by a registered dietitian/member of research team to complete a self-administered online 24-hr recall for one weekday and one weekend day. The Automated Self-Administered 24-hour (ASA24®) dietary assessment tool, a free web-based tool that enables multiple, automatically coded, self-administered 24-hour recalls, was created by the National Cancer Institute (NCI).

At baseline, each patient will receive an appointment with a registered dietitian who will conduct a nutrition assessment using the Patient-Generated Subjective Global Assessment (PG-SGA). The PG-SGA is a validated nutrition risk assessment tool that stratifies patients as malnourished, at risk of malnutrition, or well nourished^{17,18}.

During their nutrition appointment, each patient will be provided with nutrition tips based on their food record analysis. Patients will also be supplied with a whey protein supplement (Ensure Enlive, Abbot), which provides 20g/day, to optimize post-exercise muscle protein synthesis. Patients will be instructed to take the supplement once per day within one hour of completing their exercise program to enhance compliance.

A registered dietitian will be available to patients on the supervised exercise days at Total Cardiology. The dietitian will follow patient progress and offer dietary suggestions as necessary to meet patient needs.

The patients will also be asked to complete a journal (Appendix 4) detailing the quantity of nutritional supplement consumed each day.

5.2.3 Anxiety Reduction Strategies

Patients undergoing bladder surgery for cancer may be anxious and/or depressed. The control group will receive general instructions in the preoperative clinic about the perioperative care and will receive an education booklet regarding the surgery, while those in the prehabilitation group will, in addition, attend an anxiety-reduction class at the Total Cardiology program. This class will educate participants on general anxiety reduction strategies that can be implemented in hope to relieve some of these issues.

5.3 Method of Assigning Subjects to Treatment Groups

Up to 50 eligible patients will be randomly assigned to the two groups in a 1:1 ratio using a computer-generated randomization process whereby brown sealed envelopes will be prepared and opened after the patient's consent has been signed.

5.4 Blinding

Due to the nature of the study, we are unable to conceal to the research staff or participants from the different aspects of trimodal prehabilitation. However, all research data will be coded with anonymous unique identifiers so statistical analysis is performed blinded and without bias. The assessor-blinded data will not be broken on completion of the clinical study.

5.5 Supply of Protein Supplements

Participants will receive forty (40) 8oz bottles of Ensure Enlive (Abbott) Nutrition Shake (variety of flavors) to be consumed 5 days per week after exercise sessions.

5.5.1 Dosage Regimen & Administration

Patients will receive ~20 grams of whey protein via the Ensure Enlive supplement (Abbot), five days/week, and will consume the nutritional supplement within an hour of their prehabilitation exercise component. Two days will be supervised at the Total Cardiology program and three days will be unsupervised and require patients to be responsible for keeping the product at their place of residence.

5.6 Measures of Treatment Compliance

Subjects will be asked to keep a patient diary noting the date and time they participate in the exercise component of their prehabilitation program (Appendix 4). This will include a section on type of exercise completed, if the protein supplement was consumed following exercise, and for any further reflections by the patient. They will be asked to bring their patient diary to each study

visit. Staff at Total Cardiology will record attendance to the guided exercise program and anxiety reduction class.

5.7 Adverse Events Reporting

AE reporting and documentation will be carried out as outlined in the HREBA-CC SOP 404.002GR (Guidance for Submitting a Reportable Event)

6 CLINICAL ASSESSMENT & OUTCOME MEASURES

6.1 Demographics

Demographic information consisting of age, gender, occupation, and educational level will be recorded at the first visit. These factors can play a role in surgery experience and recovery.

6.2 Medical History

Aside from the initial medical examination to ensure safe participation in the prehabilitation program, a full medical history will not be recorded. Instead, the Charlson Comorbidity Index will be used to classify the overall health of the participant. Each participant will be scored on the index.

6.3 Physical Examination

Physical examinations are completed as a regular part of their pre-surgical care. During the participant's visit to the preadmission clinic (PAC), 2 weeks prior to surgery, they will undergo medical screening by an Internist and Anaesthesiologist as standard practice. Qualified staff (physician assistant, nurse, and physiotherapist) may complete an abbreviated physical exam at all other visits as part of standard practice. New abnormal physical exam findings will be documented and the participant will be referred to a physician for further examination.

Prior to the commencement of their prehabilitation program, participants undergo a medical screening exam at the Total Cardiology facility to ensure patients are medically stable.

6.4 Vital Signs & Spirometry

Blood pressure, pulse, oximetry, and incentive spirometry will be performed after resting for 5 minutes. These will be obtained on all pre-surgical visits.

6.5 Hematology & Blood Chemistry Profile

Blood work is collected during their pre-admission clinic (PAC) appointment, as a regular part of pre-surgical care. Information used in the study will include the complete blood count, glycated hemoglobin HbA1C, erythrocyte sedimentation rate, albumin, and serum C-reactive protein.

6.6 Nutrition

The Patient-Generated Subjective Global Assessment will be measured at baseline/first appointment by a Registered Dietitian.

6.7 Functional Outcomes

A number of functional outcome measures will be utilized to help determine which measures represent a valid index of recovery and are sensitive to change in our post-surgical candidates.

a. 6-minute walk test (6MWT)

The 6MWT is an exercise test used to assess aerobic capacity and to a secondary extent, functional mobility. It is a standardized test that has been validated for a variety of populations and can be useful in monitoring a person's capacity to ambulate²⁰. Briefly, the 6MWT requires the participant to ambulate for 6 continuous minutes on a 30m track with a goal of ambulating as far as they can manage in the 6 minutes. The total distance ambulated is then recorded.

b. 10m walk test (10mWT)

In contrast to the 6MWT, the 10mWT takes place by having the participant ambulate a total of 10 meters at their preferred walking speed. The time it takes to ambulate the 10m is then measured and recorded. Walking speed standards have been well established in literature and are predictive of poor health outcomes.^{21,22}

c. 30s sit-to-stand test (30s STS)

The 30s STS test is well validated for a number of conditions and age groups and correlates with lower extremity strength and function. The test requires the participant to complete as many sit-to-stand movements as possible in 30 seconds. The number of stands is then recorded.

d. Hand-grip dynamometer

A hand-grip dynamometer allows for the measurement of various types of grip strength. Grip strength has been shown to be a predictor for upper extremity strength and function, and even as a predictor for ability to carry out activities of daily living²³. For this reason, hand-grip dynamometry allows for a simple objective measure of upper extremity function.

6.8 Subjective Outcomes

a. FACT-BL Questionnaire: is a reliable and valid questionnaire that comprehensively assesses quality of life concerns pertinent to bladder cancer patients.

b. EQ-5D Questionnaire: A short, generic quality of life questionnaire.

- c. Godin Leisure Time Exercise Questionnaire: A short questionnaire on self-reported physical activity.

6.9 Traditional/Clinical Outcomes

Clinical outcomes to be used in this study will include length of hospital stay, 30d readmission rate, return to intended oncological treatment (RIOT), and postoperative complications classified according to Clavien-Dindo classification. Data is collected prospectively.

6.10 Interviews

An amendment will be provided upon the completion of the RCT which includes details of the interview recruitment process and proposed interview questions.

7 EVALUATIONS BY VISIT

7.1 Visit 1 (Baseline / Surgical consent)

1. Review the study with the subject and obtain written informed consent (Appendix 5).
2. Assign the subject a unique screening number.
3. Record demographics data.
4. Record Charlson Comorbidity Index.
5. Record chemotherapy history and schedule for ongoing treatments.
6. Record vital signs.
7. Collect functional outcome measures (as listed above).
8. Perform and record incentive spirometry.
9. Randomize subject into treatment or control group.
10. If subject is selected for treatment group, schedule subject for commencement of trimodal prehabilitation with the Total Cardiology program. If selected for control group, subject will be given a home-exercise program and nutrition information as described above.
11. Explain how to complete the study journal (exercise & nutrition compliance).
12. Explain how to complete the online 24-hr food recall.
13. Complete baseline subjective questionnaires (as listed above).

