4.6 Recruitment & Informed Consent

At RGH, patients diagnosed with bladder cancer and consent to surgery are operated on by [name], [name], [name], [name], [name], and [name]. A total of approximately 80 radical cystectomies are completed annually.

Patients will be screened by the medical team for health conditions that would prohibit participation in the program and those that are selected for prehabilitation will undergo further exercise testing at the Total Cardiology program to ensure participants are medically suitable for the intervention. The following are the steps taken for recruitment:

1. Patients who consent to elective bladder surgery that meet the inclusion/exclusion criteria will be identified and initial contact will be made by the physician assistant (RC case manager) at a scheduled appointment. The physician assistant will introduce the study to the patients.
2. If the patient decides they would like more information about the study and is willing to be contacted by the research study coordinator, the physician assistant will inform the study coordinator (JM).
3. The study coordinator (JM) will then contact the patient to explain all details of the study. If the patient is interested in participating, the coordinator will schedule a time to complete the informed consent (Appendix 5) and preoperative/baseline assessments at RGH. At this time, the patient will also be given the written informed consent to further read on their own time.
4. When the patient arrives for their scheduled appointment at RGH, they will be given all study details from the coordinator. Any further questions on their behalf will be addressed and they will be asked to sign the informed consent. Only participants who have capacity to provide fully informed consent themselves will be asked to sign a consent form.
5. Once informed consent is obtained, the patient will undergo their preoperative/baseline assessments as outlined later in this document.
6. Patient will be randomized into one of the two study groups and the study protocol will begin. Further physical and nutritional assessments will be conducted by a Physiotherapist and Registered Dietitian respectively.

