9 STATISTICAL METHODS AND CONSIDERATIONS

9.1 Quantitative Analysis

An available case analysis without imputation of missing values will be conducted. All analyses will be performed using Stata 14.1 (2015, StataCorp). All continuous variables will be reported as mean, 95% confidence interval. Categorical variables will be presented as frequency (%) and compared using Pearson's χ^2 test. A mixed effects model will be used to analyze repeated measures, including our primary outcome the 6MWT, because this method had advantages in dealing with missing data and controlling for baseline variables. A P-value <0.05 will be considered statistically significant.

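### Visit 1 lists the baseline quality-of-life and activity questionnaires after randomisation and disclosure of the arm, contrary to Section 4.6

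*Protocol*

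**What the plan says.** Section 7.1 (Visit 1) is a numbered list of 13 steps. Those that matter here are:

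- Step 7: "Collect functional outcome measures (as listed above".
- Step 9: "Randomize subject into treatment or control group".
- Step 10: "If subject is selected for treatment group, schedule subject for commencement of trimodal prehabilitation with the Total Cardiology program"; a control patient is instead handed the home programme and nutrition information.
- Step 13: "Complete baseline subjective questionnaires (as listed above". These are the instruments of Section 6.8: FACT-BL, EQ-5D and the Godin activity questionnaire.

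Section 4.6 describes the same appointment in another order. Step 5 reads "Once informed consent is obtained, the patient will undergo their preoperative/baseline assessments" and refers forward to the later description of those assessments. Step 6 follows: "Patient will be randomized into one of the two study groups and the study protocol will begin".

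Section 5.3 has the envelope opened after consent is signed and does not require baseline measures to be complete first. On blinding, Section 5.4 says "we are unable to conceal to the research staff or participants from the different aspects of trimodal prehabilitation". Section 9.1 chooses a mixed model for repeated measures partly because it helps in "controlling for baseline variables".

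**The concern.** A baseline score protects a randomised comparison only if allocation cannot have influenced it. By step 13 the patient has either been booked into a supervised programme or been sent home with an unsupervised one. Answers about wellbeing and activity can respond to that news. The score is then a post-randomisation variable, although it is labelled and used as baseline.

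Quality of life is part of the research question (Section 3.1) and a secondary objective (Section 3.3). Section 7 schedules the questionnaires only at Visits 1 and 5, so this one score is the whole pre-treatment reference. If it is adjusted for or subtracted, the reaction to allocation enters the estimated effect with its sign reversed. Patients pleased to receive prehabilitation, or controls disappointed not to, would make prehabilitation look worse than it is.

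**Working it through.** **Order of procedures**

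| Item | Section 4.6 | Section 7.1 |
|---|---|---|
| Consent | before step 5 | step 1 |
| Functional tests | step 5 (baseline assessments) | step 7 |
| Randomisation | step 6 | step 9 |
| Arm made known | after step 6 | step 10 |
| FACT-BL, EQ-5D, Godin | step 5 (baseline assessments) | step 13 |

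The two sections agree for the functional tests and conflict for the questionnaires. Section 5.3 does not settle the conflict, because it ties the envelope to consent alone.

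**Possible size**

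The protocol states no effect size, SD or power for these outcomes (Sections 4.5 and 9.2 set the sample size by funding), so there is no figure to reproduce. What follows is an illustration.

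Inputs:
- From the protocol: 25 per arm (Section 4.5) and a significance level of 0.05 (Section 9.1). Two-sided testing is assumed, since sidedness is not stated.
- Assumed: a between-arm shift *d* in the baseline score caused by knowing the arm, in SD units; a baseline-to-follow-up correlation *r*; equal variances; no true treatment effect; no lasting effect of the shift on the follow-up score.

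Formulas:
- Baseline-adjusted: bias = r × d; SE = √(2/25 × (1 − r²)).
- Change score: bias = d; SE = √(2/25 × 2(1 − r)).
- False-positive rate = Φ(−1.96 + bias/SE) + Φ(−1.96 − bias/SE).

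Standard errors for the adjusted analysis:
- r = 0.5: √(0.08 × 0.75) = 0.245 SD.
- r = 0.7: √(0.08 × 0.51) = 0.202 SD.

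Worked case, d = 0.2 and r = 0.5:
- Adjusted: bias 0.5 × 0.2 = 0.10 SD; 0.10/0.245 = 0.41; false-positive rate 0.069.
- Change score: bias 0.20 SD; SE √(0.08 × 1.0) = 0.283; 0.20/0.283 = 0.71; false-positive rate 0.109.

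| d | r | Adjusted bias (SD) | False-positive rate | Change-score bias (SD) | False-positive rate |
|---|---|---|---|---|---|
| 0.1 | 0.5 | 0.05 | 0.055 | 0.1 | 0.064 |
| 0.1 | 0.7 | 0.07 | 0.064 | 0.1 | 0.074 |
| 0.2 | 0.5 | 0.10 | 0.069 | 0.2 | 0.109 |
| 0.2 | 0.7 | 0.14 | 0.107 | 0.2 | 0.150 |
| 0.3 | 0.5 | 0.15 | 0.094 | 0.3 | 0.186 |
| 0.3 | 0.7 | 0.21 | 0.180 | 0.3 | 0.278 |

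Over a wider range (d from 0.1 to 0.5, r from 0.3 to 0.7), the adjusted bias runs from 0.03 to 0.35 SD (false-positive rate 0.051 to 0.41) and the change-score bias from 0.1 to 0.5 SD (0.060 to 0.63).

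If the questionnaires are completed before the envelope is opened, d = 0. This source of bias then vanishes and the rate stays at 0.05.

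**The case against.** The strongest reply is that Section 4.6 already gives the right order and covers all baseline assessments, so Section 7.1 is a drafting slip and not a decision to measure after allocation. Section 7.1 also never says its list is chronological: the food-recall instruction is step 12 there, whereas Section 5.2.2 places it at the time of consent. This supports describing the fault as a contradiction. It does not remove it. Consent, measurement, randomisation and hand-out run in natural order in Section 7.1, steps 9 and 10 are plainly sequential, and Section 7.1 is the list that staff would work from.

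Other points limit the size of the problem:

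- Section 9.1 does not say that the questionnaire scores will be adjusted for, or subtracted from, their own baseline. An unadjusted comparison of 8-week scores would not carry this bias. That stands, although the section names control for baseline as an advantage of its method.
- The abstract (Section 1.1) says all measures are taken at four time points, so collection only at Visits 1 and 5 rests on Section 7. Extra follow-up scores would not repair a contaminated baseline.
- The values of d and r are assumptions, and most of the adjusted biases are well below the standard error. That stands.
- Only secondary, self-reported outcomes are touched. The 6MWT and 10 m walk baselines precede randomisation, and the follow-up questionnaires remain unblinded self-report whatever the order.

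**Conclusion.** The concern holds. Followed as written, Section 7.1 yields FACT-BL, EQ-5D and Godin baselines taken after an unblinded patient knows the arm, and it contradicts Section 4.6. The order of steps is certain from the text. Whether bias arises, how large it is and which way it runs cannot be known from the protocol. For a shift of 0.1 to 0.3 SD and a correlation of 0.5 to 0.7, both assumed, the bias would be 0.05 to 0.21 SD with baseline adjustment and 0.1 to 0.3 SD with change scores. It would run against prehabilitation if patients welcome that arm. This is a modest but avoidable threat to a stated secondary objective; the primary outcome is not affected. No analysis plan can recover a pre-allocation score that was never collected.

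**What to change.** In Section 7.1, move step 13 (FACT-BL, EQ-5D and Godin) ahead of step 9. In Sections 7.1 and 5.3, state that no envelope is opened until consent is signed and all baseline questionnaires and functional tests are complete, in line with steps 5 and 6 of Section 4.6. This reorders one visit and adds no assessment, patient or cost.

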7.2 Visit 2 (Pre-admission Clinic appointment)

1. Record any adverse events and review subject diary for adverse events/compliance.
2. Reinforce home based program and review of postoperative pathway.
3. Perform and record incentive spirometry.

4. Blood work (haematology and blood chemistry profile) completed as a part of their pre-admission screening with internal medicine. No additional blood tests will be requested for study purposes.

*Note: If after review by the medical team the patient is determined to be a poor candidate for surgery, participant will be withdrawn from the study at this point.

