2.1 Risk / Benefit Analysis

2.1.1 Risk Assessment

Risks associated with an exercise program include minor aches and pains, potential for mechanical injuries, such as strains & sprains, and cardiovascular problems, such as heart arrhythmias, heart attack, or sudden cardiac arrest¹⁴. Participants undergo a medical evaluation by the Total Cardiology team to ensure participants are sufficiently healthy and medically stable to participate in a program. By tailoring the exercise programs to the individual needs of each participant, risks for mechanical injuries and exercise-associated complications are sought to be minimized. Participants are encouraged to take rests and keep physical activity within a moderate range to ensure safe participation in the program.

Typical risks associated with the use of oral nutrition supplements are rare, but include constipation, diarrhea, nausea and vomiting. Participants will undergo evaluation by a Registered Dietitian and will be monitored for adverse effects throughout the program. Pre-existing medical conditions such as diabetes may impact the ability to use nutritional supplements. These conditions will be reviewed by the Registered Dietitian and an appropriate personalized nutrition care plan will be developed in conjunction with the participant.

With respect to interviews, sharing personal experiences of surgery might make some patients uncomfortable. Participants will be advised to share only what they are comfortable with sharing. Participants will be informed that if at any time they experience feelings of anxiousness, sadness, or discomfort, they have the right to take a break during the interview, postpone the interview, or withdraw their consent to participate.

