4 STUDY DESIGN

4.1 Study Overview

This is a single center, single-blind, pragmatic randomized-control trial. There will be a total of 50 (fifty) participants in the study. Each participant will be randomly enrolled into a prehabilitation or no-prehabilitation group at time of consent for RC and those in the intervention group will undergo 8 weeks of prehabilitation through the Total Cardiology program, hosted through the Repsol Centre. Each participant, independent of study group assignment, will receive the standard treatment as outlined in the Enhanced Recovery Protocol (ERP) for Radical Cystectomies (see Appendix 1). Those enrolled in the prehabilitation group will attend 2 supervised exercise-based sessions per week and will complete a home-exercise program three times per week (total 5 exercise sessions per week). In addition, they will receive 5 protein supplement drinks per week to consume after exercise, and will attend classes on nutrition and stress/anxiety reduction techniques. Measurements will be taken at baseline, 6 weeks (as a part of their regularly scheduled pre-admission clinic appointment), 8 weeks (just prior to surgery), 4 weeks post-op, and 8 weeks post-op.

Those patients enrolled in the no-prehabilitation group will receive a general, unsupervised, home-exercise program, information regarding good nutrition. They will be followed at their regularly scheduled appointments. Again, measurements will be taken at the same time intervals as the prehabilitation group.

Screening data will be reviewed to determine subject eligibility. Subjects who meet all inclusion criteria and none of the exclusion criteria will be entered into the study.

The following treatment groups will be established:

- Standard ERP + Trimodal Prehabilitation
- Standard ERP

Total duration of subject participation will be approximately sixteen weeks. Total duration of the study is expected to be approximately 1.5 years.

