5.2 Components of Trimodal Prehabilitation

5.2.1 Exercise Program

The exercise component will consist of approximately two 60 min sessions of supervised resistance and aerobic exercises. The sessions will be under the supervision of a kinesiologist and will take place in collaboration with the Total Cardiology group out of the Repsol Sport Centre. Each participant's program will be individualized based upon the baseline fitness test and will include:

- 5 min warm-up,
- 25 min of aerobic exercise (starting at 30-40% of heart rate reserve (HRR) and progressing to 50-60% HRR as tolerated by participant),
- 25 min of resistance training (6 exercises targeting major muscle groups performed at moderate intensity), and
- 5-10 min cool-down and stretching period.
- Clear explanations & demonstrations of program by the kinesiologist

In addition, patients will be asked to carry out a 60min aerobic-based exercise program at home (i.e. walking), unsupervised, 3 days/week, and complete incentive spirometry breathing exercises 3 times/day for 10 breaths. Incentive spirometry has been shown to have beneficial effects on post-operative outcomes¹⁹ and will be included for this reason. Participants will record these additional activities in a journal that is provided to them at the start of their program.

Training intensity progression will be advised by the kinesiologist when the participant can complete aerobic exercise with mild exertion and/or when the participant can complete 15 repetitions of a given resistance exercise.

The kinesiologist will follow all participants to assess program adherence (including unsupervised sessions documented in patient's journal) and to address any barriers that may prevent ongoing participation.

The control group will receive the regular radical cystectomy information and will be asked to complete a 60min aerobic-based home exercise program, unsupervised, 5 days/week, along with incentive spirometry breathing exercises 3 times/day for 10 breaths. This group will also record their activities in a journal and a member of the research team will check in by telephone weekly to assess adherence and address any barriers or questions the patient may have.

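### Pre-operative adverse events are scheduled for recording only at weeks 6 and 8, with no common adverse-event question in the between-visit contacts, so harms may be recorded late or incompletely and capture may differ by arm.

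*Protocol*

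**What the plan says.** **Scheduled recording.** Protocol section 4.1 sets the assessment times: "Measurements will be taken at baseline, 6 weeks (as a part of their regularly scheduled pre-admission clinic appointment), 8 weeks (just prior to surgery", followed by 4 and 8 weeks after surgery. Among the pre-operative visit lists, only 7.2 (Visit 2) and 7.3 (Visit 3) contain an adverse-event item. Its wording is the same in both and is not arm-specific: "Record any adverse events and review subject diary for adverse events/compliance".

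**The diary.** Section 5.6 has patients note when they exercise and says the diary includes "a section on type of exercise completed, if the protein supplement was consumed following exercise, and for any further reflections by the patient". Section 5.2.2 adds the quantity of supplement taken. At baseline (7.1) staff are told: "Explain how to complete the study journal (exercise & nutrition compliance").

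**Contact between visits.** Section 4.1 gives the prehabilitation arm two supervised sessions a week. Under 5.2.1 the kinesiologist follows adherence and barriers, and under 5.6 Total Cardiology staff record attendance. For controls, 5.2.1 says a member of the research team "will check in by telephone weekly to assess adherence and address any barriers or questions the patient may have".

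**Risk and reporting.** Section 2.1.1 lists musculoskeletal injury and serious cardiac events as exercise risks. In its separate paragraph on oral supplements it says participants "will be monitored for adverse effects throughout the program". Section 5.7 refers adverse-event reporting and documentation to an ethics-board procedure that is not reproduced.

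**Vital signs.** Section 6.4 covers blood pressure, pulse, oximetry and incentive spirometry: "These will be obtained on all pre-surgical visits".

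**The concern.** Both arms are asked to exercise for eight weeks before major surgery, and the protocol itself names cardiac events and injuries as risks of doing so. Yet the first scheduled adverse-event record comes about six weeks in. The written aid to recall at that visit is a diary that, as described, patients are taught to use for compliance.

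The opportunities for an event to come to light in between are not the same. One arm meets staff face to face twice a week; the other speaks to someone by telephone once a week and does all its exercise unsupervised. Neither contact has a stated adverse-event question, so whether an event is noticed and passed on depends on what happens to come up.

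Two things are at stake. The first is timeliness: an event in week 1 may not reach the study record until week 6. The second is fair counting. The protocol says the results will be applied to refining the current programme (section 2) and will support organizational decisions (2.1.2). A description of harms by arm serves that purpose only if both arms were asked in the same way.

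**Working it through.** The plan gives no adverse-event rate, detection rate or related figure, so there is nothing to reproduce. The check has three parts: counts from the text, a labelled illustration, and a comparison of sections.

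**1. Counts over the 8-week pre-operative period** (sections 4.1, 5.2.1, 7.2, 7.3)

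| Item | Prehabilitation | Control |
|---|---|---|
| Scheduled adverse-event records | 2 (weeks 6 and 8) | 2 (weeks 6 and 8) |
| Staff contacts | 2 × 8 = 16 supervised sessions | 1 × 8 = 8 calls |
| Contacts with a stated adverse-event question | 0 | 0 |
| Planned exercise sessions | 16 + 3 × 8 = 40 | 5 × 8 = 40 |
| Unsupervised exercise | 3 × 60 × 8 = 1,440 min | 5 × 60 × 8 = 2,400 min |

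The number of planned sessions is equal. What differs is how much is supervised and how often, and by what means, staff are in touch. The longest recall is about 6 weeks at Visit 2 and about 2 weeks at Visit 3, in both arms.

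**2. What unequal capture would do (assumed values)**

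With 25 patients per arm (section 4.5), a true proportion *t* with an event in both arms, and capture *d*:

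- expected patients recorded = 25 × *t* × *d*
- spurious risk difference = *t* × (*d* prehabilitation − *d* control)

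The values of *t* and *d* are assumptions; none comes from the protocol.

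| *t* | Capture, prehabilitation v control | Patients recorded | Spurious difference |
|---|---|---|---|
| 20% | 90% v 90% | 4.5 v 4.5 | 0 points |
| 20% | 90% v 70% | 25 × 0.2 × 0.9 = 4.5 v 25 × 0.2 × 0.7 = 3.5 | 4 points |
| 20% | 90% v 50% | 4.5 v 25 × 0.2 × 0.5 = 2.5 | 8 points |
| 10% to 40% | 90% v 70% | 2.25 v 1.75 to 9.0 v 7.0 | 2 to 8 points |
| 10% to 40% | 90% v 50% | 2.25 v 1.25 to 9.0 v 5.0 | 4 to 16 points |

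The spurious difference is simply the assumed capture gap multiplied by the assumed rate. The table shows direction and scale, not an estimate.

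**3. Sections side by side**

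- Diary: 7.2 and 7.3 direct staff to look in it for adverse events. Sections 5.2.2, 5.6 and 7.1 each describe it, and none tells the patient to enter one there.
- Vital signs: 6.4 asks for them at every pre-surgical visit. Section 7.1 lists vital signs and spirometry as separate items; 7.2 and 7.3 list spirometry alone. The two sets of instructions disagree for Visits 2 and 3.

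**The case against.** A good deal can be said for the plan, and most of it limits the point.

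- **The diary is not the only source.** The instruction is to record events and also to review the diary. Direct enquiry at the visit comes first. This stands.
- **The control call is not about adherence alone.** It also covers barriers and patients' questions, which is close to the kinesiologist's stated task in the other arm. This stands; the stated difference is in frequency and mode.
- **Scheduled recording is identical in both arms.** A reader might infer that one arm reports to staff as events occur while the other relies on six-week recall. The text does not support that. Total Cardiology staff have no stated adverse-event recording duty, and no route from the sessions to the study record is described.
- **Unseen documents may fill the gap.** Appendix 4 may hold an adverse-event field, the reflections space could be used for one, and the procedure cited in 5.7 may say more. This stands as a limit on what can be claimed. However, that procedure is titled as guidance on submitting a reportable event, and an event has to be elicited before it can be submitted.
- **The statement about monitoring throughout the programme concerns supplements.** A reader might take it as an unkept promise about exercise harms; it sits in the supplement paragraph, and 5.2.2 does provide a dietitian on supervised days.
- **No planned estimate is biased.** Neither the objectives nor section 6.9 lists a between-arm comparison of pre-operative adverse events. With 25 per arm, even 5 against 2 events gives a Fisher p of about 0.42. This is true, but harms in a pilot are read descriptively, where one or two events alter the picture.

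The vital-signs mismatch affects both arms equally, so it is no evidence of unequal counting. It is a separate inconsistency.

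**Conclusion.** The point holds as a risk in how harms are elicited. The text establishes four things: pre-operative recording is scheduled only at weeks 6 and 8; the diary to be checked for adverse events is described without a place for them; contact between visits differs by arm (about 16 sessions against about 8 calls) with no common adverse-event question; and 6.4 disagrees with 7.2 and 7.3 on vital signs.

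It follows that exercise-period harms may be recorded late or incompletely and that capture may differ by arm. If it does, the likely direction is more events found in the prehabilitation arm, making that programme look less safe than it is. This direction assumes that what staff hear in supervised sessions finds its way into the record, which the protocol does not describe.

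A reader might go further and conclude that harms are under-counted, and unequally so. The documents do not show that: the scheduled recording is the same in both arms, and every capture rate in the illustration is assumed. The size cannot be derived from the documents. The change is still worth making, because an identical weekly question is a better method than recall over as much as six weeks and costs little.

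**What to change.** 1. Write one short adverse-event question, on one form for both arms, covering any injury, chest symptoms, stomach or bowel upset, or medical contact since the last enquiry. Ask it in the weekly control call (5.2.1) and in one Total Cardiology session each week, so that both arms are asked at the same interval. Pass positive answers to the investigator for handling under 5.7. Keep the existing records at Visits 2 and 3.
2. Add an adverse-event line to the diary described in 5.6, and mention it in the baseline instruction in 7.1. If Appendix 4 already has such a line, align 5.6 and 7.1 with it.
3. Separately, reconcile 6.4 with the Visit 2 and Visit 3 lists in 7.2 and 7.3, so that the protocol gives one instruction on vital signs.

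**Cost.** One form and a minute or two in contacts that already take place, with no new visit or staff. Recorded adverse-event counts will probably rise somewhat in both arms; the report should say that events were solicited weekly, so that the counts are not compared uncritically with studies that did not ask.
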